8.2 Criteria for Discontinuation from the Study

- Failure to complete week 4 whether due to toxicity, poor adherence or need to stop drug.
- Request by the subject to withdraw.
- Request of the primary care provider if s/he thinks the study is no longer in the best interest of the subject.
- Clinical reasons believed life threatening by the physician, even if not addressed in the toxicity management of the protocol.
- Subject judged by the investigator to be at significant risk of failing to comply with the provisions of the protocol as to cause harm to self or seriously interfere with the validity of the study results.

- At the discretion of the CCTG, FDA, investigator, or pharmaceutical sponsors.

9.0 STATISTICAL CONSIDERATIONS

9.1 General Design Issues

This is a pilot study to investigate associations between MVC treatment intensification and 1) changes in gene expression as identified by microarray analysis and 2) change in the slope of the CD4 recovery. The study is powered to detect a difference in gene expression before and after MVC. Secondary analysis will investigate whether a difference in CD4 recovery (measured by CD4 slope) is observed before and after MVC treatment intensification.

9.2 Endpoints

9.2.1 Primary

1. Differences in gene expression profiles obtained at baseline and weeks 4 and 24.

9.2.2 Secondary

1. CD4+ T-cell absolute count and percentage at baseline, weeks 4 and 24.
2. The proportion of CD4+/CD8+ T-cell immune activation, maturation, regulatory and apoptosis markers at baseline and weeks 4 and 24.
3. Grades ≥ 2 laboratory abnormalities and signs and symptoms.
4. Paired plasma to CSF ratios of MVC concentration at week 4.
5. Soluble immune activation markers in CSF at baseline and week 4.
6. HIV RNA loads in CSF at baseline and week 4.

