1.2 Secondary Objectives

- 1.2.1 To compare the rates of phase 2 CD4+ T-cell recovery prior to and during 24 weeks of MVC therapy intensification.
- 1.2.2 To evaluate the impact of MVC therapy intensification on persistent immune activation and maturation phenotype (as measured by flow cytometry) during viral suppression.
- 1.2.3 To characterize differences in the gene expression profiles associated with MVC therapy intensification in individuals receiving a PI/r- vs. NNRTI-based regimen.
- 1.2.4 To evaluate the safety and tolerability of adding MVC to a stable antiretroviral regimen as assessed by the rate of > grade 2 adverse clinical or laboratory events.
- 1.2.5 To characterize cerebral spinal fluid concentrations of MVC compared to plasma concentrations.
- 1.2.6 To evaluate the impact of MVC therapy intensification on persistent immune activation (as measured by soluble and cellular markers) in the central nervous system.

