2.4.1 Hypotheses

1. Maraviroc (MVC) concentrations in CSF will approximate 24% of the plasma C_{min} and will vary across the dosing interval.
 - a. Subjects receiving background HIV therapy containing a PI/r will achieve higher CSF MVC concentrations than those receiving not receiving a PI/r
2. MVC treatment-intensification will decrease immune activation (activated T-cells and pro-inflammatory cytokines) in the CSF.
3. Among subjects with CSF viral replication above 2 copies/mL at baseline, all will be suppressed below 2 copies/mL after 4 weeks of MVC treatment-intensification.

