5. Association between change in early immune subsets and phase 2 CD4 recovery will be assessed via Pearson's correlation analysis.

6. MVC plasma to CSF ratios at weeks 4 and 24 will be reported via descriptive statistics. Differences in MVC concentration ratios between subjects receiving a PI/r- vs. NNRTI-based background regimen will be compared via McNemar's test or paired t-tests as appropriate.

7. Descriptive statistics of CNS markers of immune activation will be reported via descriptive statistics. Differences in CNS markers of immune activation between baseline and weeks 4 and 24 will be compared cross-sectionally via McNemar's test or paired t-tests as appropriate.

8. Association between change in CNS markers of immune activation and MVC plasma to CSF ratios will be assessed via Pearson's correlation analysis.

9. Descriptive statistics of toxicity/intolerance during MVC treatment intensification will be reported via descriptive statistics. Differences in proportions of grades > 2 laboratory abnormalities and signs and symptoms will be compared via McNemar's test between time points.

10. Virologic failure during MVC treatment intensification will be reported via descriptive statistics.

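### The CSF penetration endpoint is written as plasma:CSF, the inverse of the hypothesised CSF fraction, with mean-based methods and no log scale or summary statistic specified

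*Combined protocol and SAP*

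**What the plan says.** Secondary endpoint 4 in section 9.2.2 is "Paired plasma to CSF ratios of MVC concentration at week 4". In section 9.4.3.1, item 6 says that "MVC plasma to CSF ratios at weeks 4 and 24 will be reported via descriptive statistics", and that differences in the ratios "between subjects receiving a PI/r- vs. NNRTI-based background regimen will be compared via McNemar's test or paired t-tests as appropriate". Item 8 uses the ratio again: "Association between change in CNS markers of immune activation and MVC plasma to CSF ratios will be assessed via Pearson's correlation analysis".

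The objective and the hypotheses are framed the other way round. Objective 1.2.5 is "To characterize cerebral spinal fluid concentrations of MVC compared to plasma concentrations". Hypothesis 1 in section 2.4.1 is "Maraviroc (MVC) concentrations in CSF will approximate 24% of the plasma C_{min} and will vary across the dosing interval". Its sub-hypothesis is that "Subjects receiving background HIV therapy containing a PI/r will achieve higher CSF MVC concentrations" than the remaining subjects.

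Section 9 gives no transformation for concentrations or ratios. It does not choose between mean, median and geometric mean, and it has no rule for CSF values below quantification. The opening of section 9.4.3.1 makes all tests two-sided, without multiplicity adjustment, and allows non-parametric tests where assumptions fail. Section 3.2 counts CSF MVC concentration among the sub-study's primary outcomes, plans up to 17 participants, and spreads lumbar punctures over 2 to 6 and 6 to 12 hours post dose.

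**The concern.** A ratio of two concentrations is usually right-skewed, and the arithmetic mean of plasma:CSF is not the reciprocal of the arithmetic mean of CSF:plasma. With CSF in the denominator, a few low CSF values can dominate the mean, and an unquantifiable one leaves the ratio undefined. The figure set beside 24% could therefore depend on which way the ratio is formed and which summary is chosen after the data are seen.

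The named methods, t-tests and Pearson correlation, are mean-based and sensitive to the same skew. With about 17 subjects divided by regimen there is little power to spare.

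**Working it through.** **The plan's own figure.** No power or precision is stated for the ratio. The only derived sub-study figure is the lumbar puncture yield in section 3.2: 17 × 2.5 = 42.5, given as about 43. That reproduces. A week 4 ratio exists at most once per subject, so n is at most 17.

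**Inputs.** From the documents: CSF fraction 0.24 (section 2.4.1), so plasma:CSF = 1/0.24 = 4.17; N = 17; two-sided tests. Assumed, because the documents give none of them: log-normal ratios, log SD *s* from 0.5 to 1.0, alpha 0.05, the regimen split, and the fold difference between regimens.

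**Step 1: effect on the mean.** For a log-normal ratio with geometric mean 0.24:

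- mean plasma:CSF = exp(s²/2)/0.24, and its inverse is 0.24/exp(s²/2)
- mean CSF:plasma = 0.24 × exp(s²/2)

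| s | exp(s²/2) | Mean plasma:CSF | Implied penetration | Mean CSF:plasma |
|---|---|---|---|---|
| 0.5 | 1.133 | 4.7 | 21% | 27% |
| 0.8 | 1.377 | 5.7 | 17% | 33% |
| 1.0 | 1.649 | 6.9 | 15% | 40% |

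The two directions err on opposite sides of 24%, so reversing the ratio alone does not cure the problem. On the log scale the geometric mean is 24%, or 4.17 inverted, whichever way the ratio is written.

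**Step 2: effect on the regimen comparison.** The power figures below are simulated for an independent-groups t-test on plasma:CSF, a t-test on the log ratio, and a Mann-Whitney test, with the PI/r group having the lower plasma:CSF. A CV of 50% corresponds to s = √ln(1.25) = 0.47, and a CV of 100% to s = √ln(2) = 0.83.

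| PI/r v NNRTI | s | Fold | Untransformed t | Log t | Mann-Whitney |
|---|---|---|---|---|---|
| 9 v 8 | 0.5 | 3 | 97% | 99% | – |
| 9 v 8 | 0.8 | 3 | 61% | 75% | 72% |
| 9 v 8 | 1.0 | 3 | 39% | 56% | 54% |
| 8 v 9 | 0.47 | 2 | 74% | 81% | 77% |
| 8 v 9 | 0.83 | 2 | 24% | 36% | 33% |
| 8 v 9 | 0.83 | 3 | 52% | 72% | 68% |
| 11 v 6 | 0.47 | 2 | 77% | 77% | 72% |
| 6 v 11 | 0.83 | 3 | 36% | 68% | 64% |

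With 9 v 8 the loss from not taking logs is 2, 14 and 17 points. It is nil in the 11 v 6 row. It grows when the NNRTI group, which has the higher and, untransformed, more variable ratio, is the larger one: 20 points at 8 v 9 and 32 at 6 v 11, both for a 3-fold difference with CV 100%. Mann-Whitney stays within 5 points of the log t-test in every row where it was run. Type I error of the untransformed test was 3 to 5%, so it is not inflated.

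**Step 3: whether these tests are in the plan.** They are not. Item 6 names McNemar's test or paired t-tests, but PI/r and NNRTI subjects are different people, so there are no pairs. Step 2 shows what scale would cost once an independent-groups test is substituted.

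**Step 4: whether the log ratio is the 24% quantity.** Not directly. The hypothesis refers to plasma Cmin, whereas the paired plasma samples fall 2 to 12 hours post dose and are often not trough samples.

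**The case against.** The strongest reply is that the plan commits to none of this. Item 6 says only that descriptive statistics will be reported. A median inverts exactly for an odd number of subjects such as 17, and a geometric mean always does, so the misstatement arises only if the analyst picks an arithmetic mean and then inverts it. This stands: the gap is one of specification. A reader might infer that the plan will report a biased penetration figure, but the documents do not support that because they name no mean.

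On power, the non-parametric provision in section 9.4.3.1 exists for skew of this kind. In the 9 v 8 scenarios it cuts a loss of 14 to 17 points to 2 or 3. This also largely stands, although the provision applies only when the analyst judges that assumptions fail, recovers little when spread is low, and governs tests rather than the estimate set beside 24%. A reader might want a single power-loss figure, but with no SD, split, effect size or alpha in the documents none can be given.

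The below-quantification point is hypothetical, since no MVC assay limit or expected rate is stated. This is also a secondary endpoint of a self-described pilot. Both are fair, but neither removes the mismatch between endpoint and hypothesis.

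**Conclusion.** The concern holds in a limited form. The endpoint and analysis items 6 and 8 use the inverse of the hypothesised quantity, with mean-based methods and no log scale. If an arithmetic mean were reported, penetration with a true geometric mean of 24% would read as 21% to 15% one way and 27% to 40% the other. That rests on assumed log-normality and log SD 0.5 to 1.0.

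The power argument is secondary and conditional. The loss runs from about nil to the mid-teens of points for 9 PI/r and 8 NNRTI subjects, and is larger in less favourable splits. Most of any large loss is recovered if the fallback is used.

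Two further inferences should be resisted. Changing the scale does not by itself rescue item 6, because paired tests cannot compare two independent groups. Nor does a geometric mean CSF:plasma ratio test the 24% hypothesis while the Cmin reference and the sampling times remain unreconciled. The point merits correction because CSF concentration is a primary outcome of the sub-study and the remedy is cheap.

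**What to change.** Amend section 9.2.2 item 4 and section 9.4.3.1 items 6 and 8 as follows:

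- Define the endpoint as log(CSF:plasma) and report the geometric mean ratio with its 95% CI.
- Compare PI/r with NNRTI subjects by an independent-groups test on the log ratio, accounting for time post dose, in place of McNemar's test or a paired t-test.
- Run the item 8 correlation on the log ratio.
- Treat CSF values below quantification as censored, and state the method.
- Reconcile the Cmin reference in section 2.4.1 with the 2 to 12 hour sampling in section 3.2, and set the result against 24% only after that.

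The cost is SAP wording and minor additional analysis on the same samples and assays. Accounting for time post dose uses some of the limited information from 17 subjects, so that part is not entirely free.

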9.3 Sample Size and Accrual

Sample size calculations are based on within-patient comparisons of gene expression profiles from baseline to week 24. The calculations required to make such comparisons will depend on several experimental parameters including biological variability of the samples within each class, the expected fold change to be detected, technical sensitivity of the microarray technology, and acceptable error rates of the results. As researchers in this field have shown [52], one way to ensure acceptable error rates is to control the false discovery rate (FDR), which is

equivalent to setting a minimum specificity. The FDR is the expected fraction of significant genes, which in practice, do not differ in reality. This differs from the false positive rate (FPR), which is the proportion of non-differentially expressed genes that, just by chance, appear to differ.

Determining the biological variability of the system is a difficult task, especially when there is no pre-existing data available. The ranges of conditions that can contribute to biological variability include environmental conditions, cell types, and genotypic variation [53]. Based on an extensive literature review, Zien et al. [53] conclude that a value of 0.4 provides a conservative estimate of the biological standard deviation (variability between and within classes of biological samples). We will consider biological standard deviation values of 0.4 for our power calculations. Further, we will consider a technical variation of 0.3 and 0.4.

As a conservative approach, we base the sample size calculations on the Wilcoxon Rank Sum test. This is a non-parametric procedure, in which no distributional assumptions are placed on the data. Using the on-line power calculator developed by Zien et al. [53] which computes sample sizes for microarray experiments, Table 1 provides the approximate statistical power for various biological variation, technical variations and signal-to-noise ratios. Here, we consider a Type 1 error of 0.01 and a fold change of 2. We assumed 500 hits from the 38,000 genes. Notice that these power calculations are based on the number of samples allocated to the training set (either 20 or 25 per group). The sample size calculations indicate fair power (60-80%) to find a difference in gene expression before and after maraviroc treatment.

Baseline (N)	Week 24 (N)	Biological Variation	Technical Variation	Signal-to-noise	Power
20	20	0.4	0.3	3	77%
20	20	0.4	0.4	3	68%
20	20	0.4	0.3	2	61%
25	25	0.4	0.3	3	88%
25	25	0.4	0.4	3	80%
25	25	0.4	0.3	2	75%

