9.4.1.2 Statistical Analysis

We expect to eliminate approximately 2-3% of genes in through pre-processing and filtering. The data will be randomly divided into a separate training set and a test set. 20 Baseline and 20 Week 24 samples will be used for training. The remaining 10 baseline and 10 week 24 samples will be used for testing. Using criteria such as 2-fold differences in gene expression between the two measured time points within the group of patients and a false discovery rate (the percentage of genes that will be identified by chance) of less than 2%, Significance Analysis of Microarrays (SAM) [59]) will be applied to the training set to rank order genes that best can predict differences in gene expression profiles between the two time points. The SAM method identifies genes with statistically significant changes in expression by computing a score for each gene relative to the gene specific standard deviation. Genes with scores greater than a certain (adjustable) threshold will be declared significant.

The set of highest ranking genes identified with the SAM procedure will then be clustered using unsupervised hierarchical clustering analysis [60]. The purpose of this clustering analysis is to confirm the results from SAM and to further explore the microarray data in order to possibly reveal unknown subclasses. In unsupervised hierarchical clustering, no predefined reference vectors are used and the data is not partitioned into a particular cluster in a single step. Instead, a series of partitions takes place. Next, we will use methods such as prediction analysis of microarrays (PAM) based on nearest shrunken centroids [61] to devise a cross-validated gene expression predictor for these cluster-defined classes. The PAM method is a modification of the more standard nearest-centroid method. Each class centroid is shrunk toward the overall centroids after standardizing by the within-class standard deviation. The test set will then be used for validation of our

predictor. The genes that best predict the classes will be examined for similarities such as possibly participating in common genetic pathways.

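### The 60-80% power in section 9.3 is for an unpaired test at Type 1 error 0.01, not for the FDR-below-2% gene selection in 9.4.1.2, and is probably too high for it

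*Combined protocol and SAP*

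**What the plan says.** Section 9.1 states that the study is powered for the before-and-after expression comparison, which is the only primary endpoint in 9.2.1.

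Section 9.3 introduces the calculation as paired: "Sample size calculations are based on within-patient comparisons of gene expression profiles from baseline to week 24". It describes FDR control as a way to keep error rates acceptable and distinguishes FDR from the false positive rate. As a conservative choice it then uses an unpaired test: "we base the sample size calculations on the Wilcoxon Rank Sum test". The settings are: "Here, we consider a Type 1 error of 0.01 and a fold change of 2". The number of truly changed genes is set at 500 out of 38,000. Biological SD is 0.4, technical variation 0.3 or 0.4, and signal-to-noise 2 or 3. The table gives 77, 68 and 61% at 20 per group and 88, 80 and 75% at 25 per group. The text summarises this as fair power of 60-80%.

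Section 9.4.1.2 sets out the analysis. "20 Baseline and 20 Week 24 samples will be used for training", so only the 20-per-group rows apply. SAM is run with two example criteria. One is a doubling or halving of expression from baseline to week 24. The other is "a false discovery rate (the percentage of genes that will be identified by chance) of less than 2" per cent. On the split it says: "The data will be randomly divided into a separate training set and a test set". It does not say whether SAM is run as a paired analysis or whether the split is by patient or by sample.

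**The concern.** The power table and the gene-selection rule use different error criteria. With 38,000 genes, a per-gene level of 0.01 lets through hundreds of false positives, whereas an FDR limit of 2% needs a far smaller per-gene level and so costs power. The stated 60-80% therefore does not describe the list that SAM will produce.

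That list feeds the clustering, the PAM predictor and the test-set validation. If it turns out short, a reader who relies on 60-80% could take low power for absence of a maraviroc effect, and the plan offers no way to tell the two apart.

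**Working it through.** **1. Reproduce the table.** Section 9.3 does not state sidedness or define signal-to-noise, so two assumptions are needed. An unpaired two-sided rank-sum test was simulated at per-gene level 0.01 and fold change 2. Biological noise (SD 0.4) and technical noise (SD 0.3 or 0.4) were lognormal, plus additive noise with SD √2/(signal-to-noise). Results for the six rows were 77.3, 66.6, 60.3, 87.7, 79.8 and 73.9%, against the stated 77, 68, 61, 88, 80 and 75%. All are within 2 points, which supports reading 0.01 as a two-sided per-gene level.

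**2. FDR implied by the table.** Null genes: 38,000 − 500 = 37,500. Expected false positives: 37,500 × 0.01 = 375. FDR = 375/(375 + 500 × power). To hold FDR at 2% at the stated power, the per-gene level must be 500 × power × (0.02/0.98)/37,500.

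| 20/20 row (technical, signal-to-noise) | Stated power | True positives | Implied FDR | Per-gene level for FDR 2% |
|---|---|---|---|---|
| 0.3, 3 | 77% | 385 | 49.3% | 0.00021 |
| 0.4, 3 | 68% | 340 | 52.4% | 0.00019 |
| 0.3, 2 | 61% | 305 | 55.1% | 0.00017 |

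The level needed is about 48 to 60 times stricter than 0.01.

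**3. How much pairing can recover.** The documents give no within-patient correlation. Section 9.3 separates biological from technical variation, and 9.4.1.1 ties technical variability to the assay. If the non-biological terms are independent between a patient's two arrays, only the biological variance (0.4² = 0.16) can be shared.

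- Standardised difference d, back-solved from the stated power with a two-sample t-test at 0.01: 1.096, 1.007, 0.944.
- Total SD = ln 2/d: 0.632, 0.689, 0.734.
- Largest correlation ρ = 0.16/SD²: 0.40, 0.34, 0.30.
- SD of the within-patient difference = SD × √(2(1 − ρ)): 0.69, 0.79, 0.87.

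Biological plus technical SD alone would give 95% and 87% power in the first two rows, so the signal-to-noise term must add variance.

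**4. Power at FDR 2% with 20 pairs.** The per-gene level α and power are solved jointly from α = 500 × power(α) × (0.02/0.98)/37,500. The paired effect size is d/√(2(1 − ρ)), with ρ at its ceiling.

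| Method | Row 1 | Row 2 | Row 3 |
|---|---|---|---|
| Stated (unpaired rank-sum, 0.01) | 77% | 68% | 61% |
| Unpaired t, FDR 2% | 16% | 7% | 4% |
| Paired t, 19 df, FDR 2% | 40% | 16% | 6% |
| Simulated paired SAM, no added constant | 40% | 17% | 5% |
| Simulated paired SAM, added constant | 67-70% | 40-44% | 26-27% |
| Normal approximation (optimistic) | 78% | 55% | 37% |

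The paired-t solutions have α = 0.000110, 0.000045 and 0.000017. The SAM simulation used 38,000 independent normal genes with equal variance (which favours SAM), 50 sign-flip permutations and 8 data sets per row. The added constant was the 5th percentile or the median of the gene-specific standard errors.

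Out of 500 changed genes, the table implies 305-385 found. Paired t gives 31-202 (500 × 0.063 to 500 × 0.405). SAM with the constant gives about 130-350 (500 × 0.26 to 500 × 0.70).

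**5. Sensitivity.**

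- For paired t to reach the stated power at FDR 2%, the correlation would have to be about 0.59, 0.62 and 0.64.
- Slightly higher ceilings (0.44/0.37/0.32, from a different noise scaling) give paired t 47.5/20/8% and the normal approximation 83/59/40%.
- In the noise model of step 1, with biological correlation 0.9, paired t on the log scale gives 28/9/2%.

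**The case against.** The strongest reply has four parts.

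- **The rule is not rigid.** Section 9.4.1.2 offers the 2-fold and 2% criteria as examples, uses SAM to rank genes, and calls the threshold adjustable. This is fair, but 2% is the only numerical error criterion given. Relaxing it to FDR 10% still leaves paired t at 72/48/31% at the ceiling correlations, below the stated value in every row.
- **The unpaired test is conservative, and so are other inputs.** Section 9.3 calls SD 0.4 conservative, and every changed gene is set at exactly 2-fold. At a true 2.5-fold change, paired t at FDR 2% gives 88/69/51%. This stands as a caution on size, but 9.3 bases its own figure on a 2-fold change.
- **The correlation ceiling is inferred.** The table comes from an external calculator whose definitions the documents do not give, and the ceiling assumes that all non-biological noise is independent between arrays. This also stands. A higher correlation could close the gap, so the shortfall is probable and not proven. For SAM with a constant, row 1 is only modestly short.
- **It is a pilot with a held-out test set.** Neither restores power, and the plan still makes a numerical power claim for its sole primary endpoint.

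**Conclusion.** The concern holds. It is certain that the stated power and the planned selection use different criteria and that no power is given for the selection. If 0.01 is a two-sided per-gene level, as the reproduced table indicates, the rows matching the training set imply an FDR of 49-55%, about 25 times the 2% limit.

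That 60-80% is too high for the planned analysis is probable. At the most favourable correlation inferred from the plan's inputs, only the optimistic normal approximation, and only in row 1, reaches the stated figure. The size runs from a modest gap (67-70% against 77%, SAM with a constant, row 1) to a very large one (6% against 61%, paired t, row 3). It rests on 500 true hits at exactly 2-fold, on assay noise being independent between a patient's two arrays, and on the choice of statistic.

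**What to change.** In 9.3, replace the table and its summary sentence with power for the planned paired analysis at 20 pairs. Solve the per-gene level jointly with power for FDR below 2% (500 of 38,000 changed). Show results over a stated range for the SD of the within-patient difference, or the correlation, consistent with the biological/technical split, and name the method.

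In 9.4.1.2, state that SAM is run as a two-class paired analysis and that the split is by patient, so that both samples from a patient fall in the same set. Otherwise pairs may be broken in training and the same patient may appear in both sets.

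A secondary point: say whether 2-fold is a hard cut on the observed change. If so, give power for a true change above 2-fold, because a true change of exactly 2 passes only about half the time. If not, report fold change descriptively.

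The cost is a recalculation and some SAP wording. The restated power is likely to be less favourable than 60-80%.

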9.4.3.1. Analysis of Secondary Objectives

Secondary analyses will include descriptive statistics and tests of significance between pre- and post-MVC intensification. All significance tests will be two-sided and no adjustment for multiple comparisons will be made. If necessary due to assumption failures, appropriate non-parametric statistical tests will be applied.

1. Differences in the change in CD4+ T-cell absolute count and percentage from baseline to week 4 and baseline to week 24 will be compared descriptively via separate paired Student t-tests. Repeated CD4+ T-cell absolute count measured at different time points (3 historic time-points, baseline, week 4, and week 24) will be treated as the outcome variable in a linear mixed-effects model. The primary fixed effects will include time, period (MVC vs. pre-MVC), and interaction between time and period; random effects will include both intercept and slope allowing each subject to have individual starting CD4+ T-cell counts and rate of change. Baseline covariate adjustment will be included if necessary. A significant interaction term between time and period with positive coefficient will indicate if the rate of CD4 recovery is greater during MVC compared to pre-MVC.

2. Differences in the rate of CD4+ T-cell recovery (absolute count and percentage) during MVC intensification in subjects receiving a PI/r- vs. NNRTI-based regimen will be compared via the linear mixed effects model. The fixed effects will include time, regimen (PI/r vs NNRTI), and regimen-by-time interaction; random effects will include both intercept and slope. The regimen-by-time interaction term in the model will indicate the difference in CD4+ T cell recovery rates between the two regimen groups. Baseline covariate adjustment will be included if necessary.

3. Differences in gene expression profiles between subjects receiving a PI/r vs. NNRTI-based regimen at baseline and weeks 4 and 24 will be examined by comparing the gene lists generated in the primary analysis by regimen type. If necessary, statistical modeling will include a dichotomous variable to indicate regimen type.

4. Differences in the proportion of CD4+/CD8+ T-cell immune activation, maturation, regulatory and apoptosis markers between baseline and weeks 4 and 24 will be compared cross-sectionally via McNemar's test or paired t-tests as appropriate.

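### Table 1 omits the least favourable pairing of section 9.3's own inputs (technical variation 0.4 with signal-to-noise 2), where power at the planned 20/20 training set is roughly 50-56%, below the stated 60% floor

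*Combined protocol and SAP*

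**What the plan says.** Section 9.3 (Sample Size and Accrual) fixes the biological component: "We will consider biological standard deviation values of 0.4 for our power calculations". For the technical component it says: "Further, we will consider a technical variation of 0.3 and 0.4". The test and error rate are given as "As a conservative approach, we base the sample size calculations on the Wilcoxon Rank Sum test" and "Here, we consider a Type 1 error of 0.01 and a fold change of 2".

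Table 1 is introduced as giving "approximate statistical power for various biological variation, technical variations and signal-to-noise ratios". The signal-to-noise values, 3 and 2, appear only as table entries. With biological variation 0.4 throughout, the printed power is:

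| Technical variation | Signal-to-noise | 20/20 | 25/25 |
|---|---|---|---|
| 0.3 | 3 | 77% | 88% |
| 0.4 | 3 | 68% | 80% |
| 0.3 | 2 | 61% | 75% |
| 0.4 | 2 | not printed | not printed |

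The section sums up: "The sample size calculations indicate fair power (60-80%) to find a difference in gene expression before and after maraviroc treatment". Section 9.4.1.2 then settles which sample size applies: "20 Baseline and 20 Week 24 samples will be used for training".

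**The concern.** Two technical variations and two signal-to-noise values make four combinations, and the one left out is the worst at both sample sizes. Section 9.3 itself says that determining biological variability is difficult without pre-existing data. The reader therefore depends on this grid to see how far power could fall under inputs the authors thought plausible.

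It is also the only power statement in the protocol, and section 9.1 says the study is powered for the gene-expression comparison. If the worst corner lies below 60%, the summary gives a lower limit that the section's own inputs do not support.

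**Working it through.** **Step 1: direction, from the table alone.** Raising technical variation from 0.3 to 0.4 at signal-to-noise 3 lowers printed power from 77% to 68% at 20/20 and from 88% to 80% at 25/25. The same change at signal-to-noise 2 must start from 61% at 20/20 and go down. So the missing 20/20 cell is below 61%, and only the size of the drop needs estimating.

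**Step 2: size, from the table alone.**
- Additive extrapolation at 20/20: 68 + 61 - 77 = 52%.
- Probit scale at 20/20: 0.468 + 0.279 - 0.739 = 0.008, which corresponds to 50%.
- Additive extrapolation at 25/25: 80 + 75 - 88 = 67%.

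**Step 3: reproduce the printed figures.** Inputs from section 9.3 and Table 1 are the rank-sum test, Type I error 0.01, fold change 2, biological SD 0.4, technical SD 0.3 or 0.4, and signal-to-noise 3 or 2. Two inputs are not given and are assumed: a two-sided test (section 9.4.3.1 states this only for the secondary analyses) and the form of the noise. The model is

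expression = mu x exp(0.4 Z1 + tech x Z2) + e,

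with mu = 1 at baseline and 2 at week 24, Z1 and Z2 standard normal, and e normal with SD = sqrt(2) / signal-to-noise. Here sqrt(2) is the geometric mean of the two signal levels. The two groups are treated as independent. Power by simulation, with 200,000 replicates per cell:

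| n per group | Technical | Signal-to-noise | Printed | Normal approximation | Exact critical value |
|---|---|---|---|---|---|
| 20 | 0.3 | 3 | 77% | 76.7% | 77.7% |
| 20 | 0.4 | 3 | 68% | 66.8% | 68.0% |
| 20 | 0.3 | 2 | 61% | 60.3% | 61.5% |
| 25 | 0.3 | 3 | 88% | 87.9% | 88.3% |
| 25 | 0.4 | 3 | 80% | 80.0% | 80.6% |
| 25 | 0.3 | 2 | 75% | 73.9% | 74.6% |

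All six cells agree to within about 1 point.

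**Step 4: the missing cell under the same model.**
- 20/20, technical 0.4, signal-to-noise 2: 52.6% (normal approximation) to 53.8% (exact).
- 25/25, same inputs: 66.1% to 67.0%.

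**Step 5: sensitivity to the inferred model.** Other noise definitions, with the rejection threshold tuned to come as close to the table as possible, give about 53-56% for the missing 20/20 cell. Scaling the noise to the arithmetic mean signal at two-sided 0.01 gives about 50%. That variant does not reproduce the table (about 57% where 61% is printed), so it carries no weight here. The low end of 50% rests on the probit extrapolation in Step 2.

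The plausible range for the missing 20/20 cell is therefore about 50-56%, with a best estimate of 52-54%.

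**The case against.** The strongest reply is that nothing printed is wrong, and that is so. All six cells reproduce, and the 20/20 rows, 61-77%, round fairly to 60-80%. The 25/25 rows reach 88%, outside the quoted range, so they have not inflated the summary. The section promises power for various inputs, not a full cross, and varying one input at a time from a reference case is a common layout. Signal-to-noise 2 is a table entry, not a value that the text commits to. These points make this an incompleteness in the summary and not an arithmetic error. They do not restore the floor, because both inputs to the missing row are the section's own.

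A second reply is that the calculator's noise model and sidedness are undocumented. This also stands, and it is why the size is given as a range. The conclusion that the cell is below 60% does not depend on the model: the table-only extrapolations and the fitted variants all fall between 50% and 56%.

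A reader might infer that the planned screen would miss about half of the genes that truly change 2-fold. The documents do not support that. The figure is power for an unpaired rank-sum test at 0.01 per gene, used in section 9.3 as a conservative stand-in. Section 9.4.1.2 plans SAM with a false discovery rate below 2% and a 2-fold criterion, on samples from the same patients, and its sensitivity was not calculated. Pairing alone could move the figure either way. As an illustration, a signed-rank test under the same model gives about 48%, 56%, 60% and 65% for the missing cell at assumed within-patient biological correlations of 0, 0.5, 0.7 and 0.9. The documents give no correlation. This limits what the figure means, but section 9.3 presents its range as the output of the rank-sum calculation, and on that basis the range is incomplete.

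**Conclusion.** The point holds as a correction to the stated range. Across the inputs section 9.3 uses, and at the 20/20 training set that section 9.4.1.2 plans, rank-sum power extends down to roughly 50-56% (best estimate 52-54%). That is about 6 to 8 points below the stated 60% floor (60 - 54 = 6; 60 - 52 = 8). The upper end at 20/20 is the printed 77%. At 25/25 the missing cell is about 66-67%, below the lowest printed 25/25 value of 75% but inside the stated range.

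That the cell is below 61% needs only the pattern in the printed table. The size rests on an inferred additive-noise model and a two-sided test at 0.01, both chosen because they reproduce the six printed cells. Nothing here shows that the design is invalid, that the sample size should change, or what the sensitivity of the SAM analysis will be. The study is described as a pilot, so the consequence is a lower limit that should be stated correctly.

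**What to change.** Run the same on-line calculator for biological variation 0.4, technical variation 0.4 and signal-to-noise 2, and add the row to Table 1. Restate the summary sentence for the planned training set of 20 baseline and 20 week-24 samples, using the lower limit that the run returns (expected in the low 50s) and the upper limit of 77%. The lower limit should not be written into the protocol before that run, because the figure given here comes from an inferred model.

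Add a clause saying that this is power for the unpaired rank-sum surrogate at 0.01 and not for the SAM analysis. The 25/25 rows can stay if labelled as not the planned training set.

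The cost is one calculator run and a few words in section 9.3. The drawback is that the stated power becomes less favourable. Sample size, conduct and analysis are unaffected.
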